## **GLOSSARY OF ABBREVIATIONS**

BASEC	Business Administration System for Ethical Committees
CRF	Case report form
FOPH	Federal Office of Public Health
HRA	Humane Research Act
HRO	Ordinance on Human

## 1 BACKGROUND AND PROJECT RATIONALE

The spectrum of symptoms from which back patients suffer is wide-ranging. Symptoms can be constant or intermittent, are partly movement- and exertion-dependent, and include pain, sensory disturbances, mobility restrictions, and loss of strength (Huang and Sengupta 2014). Based on the duration of the symptoms, back pain is classified as chronic, sub-acute or acute. Furthermore, a subdivision can be divided into specific back complaints, with a recognizable anatomical or physiological cause, or non-specific back complaints, with no recognizable anatomical or physiological cause (Eckardt 2012, Ehrlich and Khaltaev 1999). Possible specific back problems are a herniated disc or narrowing of the spinal canal. In this case, one or more spinal nerves can be threatened/pinched, causing the patient to suffer from radiating symptoms in the supply area of the affected nerve. These radiculopathy symptoms vary in severity and duration and can in turn be dependent on movement and exertion. The longer and more intensively the spinal nerve is compressed, the more pronounced the symptoms manifest themselves and the longer it takes for the regeneration of the nerve tissue and the associated reduction of symptoms. The sensory disturbances in the supply area can develop to numbness, the reduction in strength to complete paralysis of the corresponding characteristic muscles.

The symptoms of pain, sensory disturbances and loss of strength limit the patient's ADL functions and ability to work (Hartvigsen et al. 2017). Therefore, rapid recovery and restoration of function is also important from a socio-economic point of view. The method of choice for non-acute threatening findings is physiotherapeutic treatment. Physiotherapy is prescribed by doctors in Switzerland. The medical clinical diagnosis and findings include an anamnesis, imaging procedures (Bertilson et al. 2010), a functional examination of the sensory system (sensitivity test) (Tschugg et al. 2017, Iversen et al. 2013), motor skills (force measurement) (Rainville et al. 2003) and nerve mobility (Tawa, Rhoda and Diener 2017). If necessary, the clinical diagnosis of nerve root compression is confirmed or excluded with imaging techniques. In the case of acutely threatening symptoms, such as cauda equina syndrome, surgical decompression of the affected nerve is often carried out, followed by physiotherapeutic follow-up treatment.

For the rehabilitation process, therapy planning and protection vis-à-vis health insurers, proof of efficient and goal-oriented physiotherapeutic therapy through appropriate assessments is indispensable. Although physiotherapeutic (follow-up) treatment for back patients is successful, some of the assessments and treatment methods are insufficiently validated and standardised.

The aim of this prospective observational study is to objectify and validate the pain and functional parameters motor and sensory function. In addition, we would like to record these over time in order to evaluate possible connections with physical impairment and physiotherapeutic objectives.

From the point of view of evidence-based practice, the inventory of the relationships between pain and objective functional parameters is intended to substantiate and optimize physiotherapeutic (after) treatment.

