## 2 PROJECT OBJECTIVES AND DESIGN

### 2.1 Hypothesis and primary objective

The following working and null hypotheses are to be statistically proven or discarded.

Pain Drawing (VAS)

---

H0 There is no correlation between pain and physical impairment and health-related quality of life.

H1 There is a correlation between pain and physical impairment and health-related quality of life.

H0 There is no correlation between pain and activity diary.

H1 There is a correlation between pain and activity diary.

H0 There is no correlation between pain and strength and muscle fiber alignment.

H1 There is a correlation between pain and strength and muscle fiber alignment.

H0 There is no correlation between pain and trunk mobility and trunk fluctuations.

H1 There is a correlation between pain and trunk mobility and trunk fluctuations.

H0 There is no correlation between pain and sensory activity.

H1 There is a correlation between pain and sensory activity.

---

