## 2.2 Primary and secondary endpoints

The primary objective of this observational study is to objectify the subjective parameters indicated by the patient (pain, physical impairment, health-related quality of life, activity diary) and the objective parameters measured by the investigator (strength, trunk mobility and trunk fluctuations, sensory, neurodynamics, thickness of the subcutaneous fat layer, muscle fiber alignment and physiotherapeutic objectives).

The secondary objective includes the evaluation of possible relationships between the subjective and objective parameters.

Subjective parameters and their objectification:

- **health-related quality of life**

The health-related quality of life prevailing at the time of measurement is assessed using the German version of the SF-36. The patient fills out the questionnaire independently during the measurement appointment, without being influenced. The examiner adds up the total score achieved and transfers the value to the patient's data sheet.

Objectification of health-related quality of life:

SF-36 Questionnaire, German Version

- **Physical impairment**

The physical impairment prevalent at the time of measurement is assessed using the German version of the Oswestry Disability Questionnaire (ODQ). The patient fills out the questionnaire independently during the measurement appointment, without being influenced. The examiner adds up the total score achieved and transfers the value to the patient's data sheet.

Objectification of physical impairment:

Oswestry Disability Questionnaire, German version

- **Pain**

The pain radiation and the intensity of pain are subjectively assessed by the patient. For this purpose, he is given a sheet with a body chart (pain drawing). With 3 different colors (red = pain, yellow = paresthesia, green = numbness), the patient draws the current sensations at this measurement time. In addition, the patient is surveyed using the visual analogue scale (VAS 0 (no complaints) – 10 (maximum complaints)) to record the intensity of the complaints.

Objectification of radiation area:

The pain drawings are scanned and evaluated with the MATLAB software ([www.ch.mathworks.com](http://www.ch.mathworks.com)). Here, the radiation area is quantified as a percentage of the total body surface.

Objectification intensity:

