### - **Force**

The maximum isometric force and the force development of the muscles supplied by the affected spinal nerve are tested in a standardized starting position. For this purpose, a dynamometer held by hand by the tester is used. The patient is asked to press against the examiner's hand as hard and as long as possible. In addition, a superficial electromyography is performed, in which the electrodes are glued to the points provided for this purpose on the skin. To ensure that the test situation remains isometric, the examiner applies exactly as much force as the patient is willing to deploy. The test is carried out 3 times in a row with a 30-second break. The values are transferred to the data sheet. The measurements take place on both sides, starting with the subjectively weaker side.

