## **4 STATISTICS AND METHODOLOGY**

### **4.1. Statistical analysis plan**

The required number of subjects was determined a priori with G\*Power (version 3.1.9.2; Franz Faul University of Kiel, Germany). The following design specifications were used: statistical test = Correlation Type of Power Analysis 'Computer required sample size – given  $\alpha$ , power and effect size'; tails = two; effect size = 0.5;  $\alpha$  = 0.05; power = 0.95. The target number of subjects was  $n$  = 42 based on these design specifications. The SPSS version 24 software is used for statistical data analysis (IBM, Armonk, NY, USA).

The data are first checked for normal distribution with the 'Shapiro-Wilk test'. The normally distributed data are analysed by means of parametric test procedures. Non-normally distributed data as well as non-metric data are checked with non-parametric tests. The correlations are recorded using the 'Pearson Correlation tests' and 'Spearman Correlation tests'.

Correlations between the subjective parameters (pain, physical impairment, activity diary), between the objective parameters (strength, balance, sensory, neurodynamics, muscle thickness

and physiotherapeutic objectives), as well as between the subjective and objective parameters are of interest and should be calculated.

The following working (H1) and null hypotheses (H0) are statistically proven or rejected:

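### Sections 2.1 and 2.2 disagree on whether the correlations are primary or secondary, and the background aim to validate the measures has no matching analysis

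*Combined protocol and SAP*

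**What the plan says.** Section 1 (Background and project rationale) gives the motive: "some of the assessments and treatment methods are insufficiently validated and standardised". It then states the aim, which is to "objectify and validate the pain and functional parameters motor and sensory function".

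Section 2 gives two accounts of what is primary:

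- The section headed "2.1 Hypothesis and primary objective" contains only pairs of null and alternative hypotheses about correlation. Nothing else in it could be a primary objective.
- Section 2.2 says: "The primary objective of this observational study is to objectify the subjective parameters indicated by the patient", and extends this to the parameters measured by the investigator. It continues: "The secondary objective includes the evaluation of possible relationships between the subjective and objective parameters".

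The rest of section 2.2 goes through the parameters and, under an 'objectification' label, names the questionnaire, device or scoring method that turns each into a number.

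Section 4.1 bases n = 42 on a two-sided correlation test (effect size 0.5, alpha 0.05, power 0.95). It plans a Shapiro-Wilk check, unspecified parametric or non-parametric tests, and Pearson or Spearman correlations. Correlations within and between the subjective and objective sets "are of interest and should be calculated", and the correlation hypotheses are listed again. Sections 4.2 and 7.2 also describe the output as relationships or correlations.

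For isometric force, section 2.2 requires repeated trials on both sides: "The test is carried out 3 times in a row with a 30-second break". No analysis of these repeats is planned.

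**The concern.** Two things do not fit together. First, a reader cannot tell which objective is primary: the correlations are primary by the heading of 2.1 and secondary by the text of 2.2. This affects how the results may be reported and which objective n = 42 is meant to serve.

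Second, the background promises validation because existing assessments are said to lack it. A validation claim needs at least one of reliability, measurement error, agreement with a reference, responsiveness, or correlations judged against an expectation stated in advance. The plan has none of these. Followed as written, it would yield correlations that could be reported as validation without supporting it.

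A related difficulty is that a weak correlation involving force could mean little association or a noisy measurement. The dynamometer is held by hand and the examiner matches the patient's effort, so measurement error is a fair question, and the plan says nothing about estimating it.

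**Working it through.** **1. Objectives against analyses**

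| Stated purpose | Where | Matching analysis |
|---|---|---|
| Validate pain, motor and sensory parameters | Section 1 | None |
| Objectify the parameters (primary) | Section 2.2 | Instrument or scoring named; no statistic attached |
| Relationships between subjective and objective parameters (secondary) | Section 2.2 | Correlations, section 4.1 |
| Correlation hypotheses (under a heading that includes the primary objective) | Section 2.1 | Correlations, section 4.1; basis of n = 42 |

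'Validate' occurs in the section 1 aim and not in the section 2.2 objective. The two statements should be kept apart.

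**2. The plan's own sample size**

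Inputs from section 4.1: r = 0.5, two-sided alpha 0.05, power 0.95. Using the noncentral t (point-biserial) model with df = n − 2 and noncentrality √(n·r²/(1 − r²)):

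- n = 42: noncentrality = √(42 × 0.25/0.75) = 3.742; power 0.9545.
- n = 41: power 0.94995, just short of 0.95.

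So 42 reproduces. It sizes a test of zero correlation and nothing else.

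**3. What rejecting zero shows at n = 42**

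- Critical value: t(0.975, 40) = 2.021, so |r| = 2.021/√(40 + 2.021²) = 0.304. Shared variance is 0.304² = 0.093, about 9%.
- Interval around an observed r = 0.5 (Fisher z): 0.549 ± 1.96/√39 = 0.235 to 0.863, which back-transforms to 0.23 to 0.70.
- A correlation is unchanged when one measure is shifted or rescaled (for example y to 2y + 10), so it cannot show agreement.

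A significant result is therefore compatible with a weak link and says nothing about bias or repeatability.

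**4. Precision of a force repeatability analysis**

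Inputs: k = 3 trials (section 2.2, Force) and n = 42 (section 4.1). The ICC values are assumed. With F = (1 + (k − 1)·ICC)/(1 − ICC) on n − 1 and n(k − 1) df, each limit is (F* − 1)/(F* + k − 1), where F* is F divided or multiplied by the relevant 97.5% F quantile.

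- ICC 0.80, n = 42: F = 2.6/0.2 = 13, df 41 and 84. Lower F* = 13/1.664 = 7.81, giving 0.69. Upper F* = 13 × 1.749 = 22.73, giving 0.88.
- ICC 0.90, n = 42: F = 2.8/0.1 = 28, giving 0.84 to 0.94.
- ICC 0.80, n = 14 (assumed: three equal muscle groups, 42/3): F = 13, df 13 and 28. F* = 13/2.409 = 5.40 and 13 × 2.853 = 37.09, giving 0.59 to 0.92.

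The smaller n matters because section 2.2 tests the muscles supplied by the affected nerve and its neurodynamics text lists levels from L2 to S1, so the muscle can differ between patients. Pooling muscles would add between-muscle variance and could inflate the ICC.

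**5. Illustration of attenuation (assumed reliabilities)**

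If 0.5 were the error-free correlation, the observable value would be 0.5 × √(rel_x × rel_y). Power at n = 42 uses the model of step 2.

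| Reliabilities | Observable r | Power |
|---|---|---|
| 1 and 1 | 0.50 | 0.95 |
| 0.8 and 0.8 | 0.40 | 0.79 |
| 0.7 and 0.7 | 0.35 | 0.66 |

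Section 4.1 does not say whether 0.5 is the error-free or the observed correlation. If it is the observed one, attenuation is already included and no power is lost.

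**The case against.** The best defence is that nothing is missing. Section 2.1 files the correlation hypotheses under its heading on the primary objective. On that reading the primary question has hypotheses, a test and a sample size, and 2.2 is merely mislabelled. In 2.2 'objectify' is used operationally: it names the instrument that quantifies each parameter, which is achieved by measuring and reporting and needs no ICC. Correlations among related measures are also a recognised, if limited, form of convergent-validity evidence.

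Much of this stands. A reader might infer that the study would end with no result for its primary objective, or that its primary question cannot be answered. The documents do not support either: under 2.1 there is a tested primary question, and under 2.2 the objective amounts to quantification. The defence does not remove the contradiction between 2.1 and 2.2. It also does not supply what convergent validity needs, an expected direction and size stated beforehand.

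A further fair objection is that three trials 30 seconds apart cannot validate pain, motor and sensory measures. That is correct. They show within-session repeatability of force only, not validity and not reliability between days or examiners. Such an analysis can support the correlations but should not be called the analysis of the primary objective.

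**Conclusion.** The point holds as a contradiction in the stated objectives together with an unsupported word in the aim. The protocol must settle whether the correlations are primary. As planned, the study can report associations (|r| above about 0.30 reaches significance at n = 42) but cannot support a conclusion that any measure has been validated, beyond limited convergent evidence without pre-set criteria.

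The sample size is not in dispute: 42 follows from its stated inputs. A reader might take the attenuation figures as a real loss of power. They rest on reliabilities that the documents do not give and on treating 0.5 as error-free, so they are only an illustration. Nor should useful precision for a force ICC be taken as assured: 0.69 to 0.88 assumes that all 42 patients can be analysed on a common muscle, and about 0.59 to 0.92 is more realistic if they split into groups of around 14.

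This should be corrected, but it does not invalidate the study.

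**What to change.** 1. **Section 2.2:** make the correlations, on which n = 42 is based, the primary objective, consistent with 2.1. Describe objectification as the method of measurement.
2. **Section 1:** delete 'validate' or limit it to what is analysed. If correlations are to count as convergent-validity evidence, state the expected direction and minimum size for the pairs concerned.
3. **Section 4.1:** add, as a supporting and not a primary analysis, the within-session ICC with 95% interval, standard error of measurement and minimal detectable change of isometric force from the three required trials. Compute these within muscle group, at one visit and side named in advance; every side at every visit would give 2 × 6 = 12 sets of estimates with none designated as principal. Describe the result as within-session repeatability only, and use it when interpreting weak force correlations.

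Cost: an amendment to the wording and a small extra analysis, with no new visits, devices or patients. All three trial values per side must be kept in the dataset, not only a mean or maximum. The downside is a narrower validation claim, and wide intervals if patients are split by muscle.

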## 2 PROJECT OBJECTIVES AND DESIGN

### 2.1 Hypothesis and primary objective

The following working and null hypotheses are to be statistically proven or discarded.

Pain Drawing (VAS)

---

H0 There is no correlation between pain and physical impairment and health-related quality of life.

H1 There is a correlation between pain and physical impairment and health-related quality of life.

H0 There is no correlation between pain and activity diary.

H1 There is a correlation between pain and activity diary.

H0 There is no correlation between pain and strength and muscle fiber alignment.

H1 There is a correlation between pain and strength and muscle fiber alignment.

H0 There is no correlation between pain and trunk mobility and trunk fluctuations.

H1 There is a correlation between pain and trunk mobility and trunk fluctuations.

H0 There is no correlation between pain and sensory activity.

H1 There is a correlation between pain and sensory activity.

---

#### Physical impairment, health-related quality of life (ODQ, SF-36)

H0 There is no correlation between physical impairment, health-related quality of life and activity diary.

H1 There is a correlation between physical impairment, health-related quality of life and activity diary.

H0 There is no correlation between physical impairment, health-related quality of life and strength.

H1 There is a correlation between physical impairment, health-related quality of life and strength.

H0 There is no correlation between physical impairment, health-related quality of life and trunk mobility and trunk fluctuations.

H1 There is a correlation between physical impairment, health-related quality of life and trunk mobility and trunk fluctuations.

H0 There is no correlation between physical impairment, health-related quality of life and sensory perception.

H1 There is a correlation between physical impairment, health-related quality of life and sensory perception.

H0 There is no correlation between physical impairment and thickness of the subcutaneous fat layer and muscle fiber alignment.

H1 There is a correlation between physical impairment and thickness of the subcutaneous fat layer and muscle fiber alignment.

---

#### Strength (isometric force measurement of the affected characteristic muscles)

H0 There is no correlation between isometric force and trunk mobility and trunk fluctuations.

H1 There is a correlation between isometric force and trunk mobility and trunk fluctuations.

H0 There is no correlation between isometric force and sensing.

H1 There is a correlation between isometric force and sensing.

H0 There is no correlation between isometric force and thickness of the subcutaneous fat layer and muscle fiber alignment.

H1 There is a correlation between isometric force and thickness of the subcutaneous fat layer and muscle fiber alignment.

H0 There is no correlation between isometric strength and physiotherapeutic objective.

H1 There is a correlation between isometric strength and physiotherapeutic objectives.

H0 There is no correlation between isometric strength and physical impairment and health-related quality of life.

H1 There is a correlation between isometric strength and physical impairment and health-related quality of life.

---

#### Trunk mobility and trunk fluctuations

H0 There is no correlation between trunk mobility and trunk fluctuations and sensor technology.

---

H1	There is a correlation between trunk mobility and trunk fluctuations and sensor technology.
H0	There is no correlation between trunk mobility and trunk fluctuations and physiotherapeutic objectives.
H1	There is a correlation between trunk mobility and trunk fluctuations and physiotherapeutic objectives.
H0	There is no correlation between trunk mobility and trunk fluctuations and thickness of the subcutaneous fat layer and muscle fiber alignment.
H1	There is a correlation between trunk mobility and trunk fluctuations and thickness of the subcutaneous fat layer and muscle fiber alignment.

## 2.2 Primary and secondary endpoints

The primary objective of this observational study is to objectify the subjective parameters indicated by the patient (pain, physical impairment, health-related quality of life, activity diary) and the objective parameters measured by the investigator (strength, trunk mobility and trunk fluctuations, sensory, neurodynamics, thickness of the subcutaneous fat layer, muscle fiber alignment and physiotherapeutic objectives).

The secondary objective includes the evaluation of possible relationships between the subjective and objective parameters.

Subjective parameters and their objectification:

- **health-related quality of life**

The health-related quality of life prevailing at the time of measurement is assessed using the German version of the SF-36. The patient fills out the questionnaire independently during the measurement appointment, without being influenced. The examiner adds up the total score achieved and transfers the value to the patient's data sheet.

Objectification of health-related quality of life:

SF-36 Questionnaire, German Version

- **Physical impairment**

The physical impairment prevalent at the time of measurement is assessed using the German version of the Oswestry Disability Questionnaire (ODQ). The patient fills out the questionnaire independently during the measurement appointment, without being influenced. The examiner adds up the total score achieved and transfers the value to the patient's data sheet.

Objectification of physical impairment:

Oswestry Disability Questionnaire, German version

- **Pain**

The pain radiation and the intensity of pain are subjectively assessed by the patient. For this purpose, he is given a sheet with a body chart (pain drawing). With 3 different colors (red = pain, yellow = paresthesia, green = numbness), the patient draws the current sensations at this measurement time. In addition, the patient is surveyed using the visual analogue scale (VAS 0 (no complaints) – 10 (maximum complaints)) to record the intensity of the complaints.

Objectification of radiation area:

The pain drawings are scanned and evaluated with the MATLAB software ([www.ch.mathworks.com](http://www.ch.mathworks.com)). Here, the radiation area is quantified as a percentage of the total body surface.

Objectification intensity:

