#### Pain Drawing (VAS)

---

H0 There is no correlation between pain and physical impairment and health-related quality of life.  
H1 There is a correlation between pain and physical impairment and health-related quality of life.

H0 There is no correlation between pain and activity diary.  
H1 There is a correlation between pain and activity diary.

H0 There is no correlation between pain and strength and muscle fiber alignment.  
H1 There is a correlation between pain and strength and muscle fiber alignment.

H0 There is no correlation between pain and trunk mobility and trunk fluctuations.  
H1 There is a correlation between pain and trunk mobility and trunk fluctuations.

H0 There is no correlation between pain and sensory activity.  
H1 There is a correlation between pain and sensory activity.

---

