#### Physical impairment (ODQ), health-related quality of life (SF-36)

---

H0 There is no correlation between physical impairment, health-related quality of life and the activity diary.  
H1 There is a correlation between physical impairment, health-related quality of life and the activity diary.

H0 There is no correlation between physical impairment, health-related quality of life and strength.  
H1 There is a correlation between physical impairment, health-related quality of life and strength.

H0 There is no correlation between physical impairment, health-related quality of life and trunk mobility and trunk fluctuations.  
H1 There is a correlation between physical impairment, health-related quality of life and trunk mobility and trunk fluctuations.

H0 There is no correlation between physical impairment, health-related quality of life and sensory perception.  
H1 There is a correlation between physical impairment, health-related quality of life and sensory perception.

H0 There is no correlation between physical impairment, health-related quality of life, and subcutaneous fat layer thickness and muscle fiber alignment.  
H1 There is a correlation between physical impairment, health-related quality of life and thickness of the subcutaneous fat layer and muscle fiber alignment.

---

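### The SF-36 is reduced to one examiner-added total, so a correlation in any of the six quality-of-life hypotheses cannot be attributed to physical or mental health

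*Combined protocol and SAP*

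**What the plan says.** Section 2.2 names the instrument: "The health-related quality of life prevailing at the time of measurement is assessed using the German version of the SF-36". The patient completes it alone at the visit, and then "The examiner adds up the total score achieved and transfers the value to the patient's data sheet". The ODQ paragraph directly below repeats that scoring sentence word for word. One SF-36 value per visit therefore reaches the data sheet.

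Section 4.1 tests 17 hypotheses (5 on pain, 5 on physical impairment and quality of life, 4 on force, 3 on trunk measures). Health-related quality of life enters six of them:

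- one in the pain group: "There is no correlation between pain and physical impairment and health-related quality of life";
- all five in the ODQ/SF-36 group (activity diary, strength, trunk measures, sensory measures, fat layer with fibre alignment), for example "There is no correlation between physical impairment, health-related quality of life and strength".

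None of the six says which SF-36 score is meant. The sentence in 4.1 listing what will be correlated, "Correlations between the subjective parameters (pain, physical impairment, activity diary", leaves quality of life out of the subjective parameters. The method is one coefficient per pair of variables: "The correlations are recorded using the 'Pearson Correlation tests' and 'Spearman Correlation tests".

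The documents name no SF-36 version, scoring manual, scale, summary score, recoding step, score direction or rule for a skipped item. Section 4.2 excludes incomplete data from individual assessments, described as aborted tests, and does not say whether a questionnaire with one blank item counts as such.

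**The concern.** Section 2.2 makes objectifying the subjective parameters, quality of life among them, the primary objective. Section 1 justifies the study partly by noting that some current assessments lack validation and standardisation. A hand-added total with no stated algorithm sits badly with that aim.

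The practical loss is in interpretation. If the total correlates with isometric strength, the reader will want to know whether stronger patients report better physical health, better mental health or both. If it does not, the reader will want to know whether one part was related and the other diluted it. A single value per visit answers neither question, and no later choice between Pearson and Spearman recovers the answer. Because no direction is stated, the sign of a coefficient cannot be read from the plan either. The tests are two-sided, so this affects the reading of a result and not the test itself.

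**Working it through.** **1. The plan's own figure.** Inputs from section 4.1: correlation 0.5, two-sided, alpha and power as in "0.05; power = 0.95", stated n = 42. Under the point-biserial t model, the noncentrality is r√n / √(1 − r²) = 0.5 × √42 / √0.75 = 3.74 on 40 df, and power is 0.9545. The stated 42 is reproduced. (The exact bivariate-normal model needs 46 and gives power 0.935 at n = 42; that is a separate matter.) The SF-36 scoring rule does not enter this calculation.

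**2. What a single total can show.** Assumptions, none from the documents: the total is the sum of two equal-variance parts, physical and mental, which correlate g with each other and correlate a and h with some other measure such as strength. Then

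r(total) = (a + h) / √(2 + 2g).

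Only a + h appears. With g = 0.5 the denominator is √3 = 1.732, and:

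| a (physical) | h (mental) | r(total) |
|---|---|---|
| 0.50 | 0.25 | 0.433 |
| 0.25 | 0.50 | 0.433 |
| 0.375 | 0.375 | 0.433 |

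Three different clinical statements give the same coefficient. This does not depend on how carefully the items are added.

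**3. Does the total always weaken the correlation?** Keep a = 0.5 and vary the rest. Power is at n = 42 in the plan's own model.

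| g | h | r(total) | power |
|---|---|---|---|
| 0 | 0 | 0.5/√2 = 0.354 | 0.667 |
| 0.7 | 0 | 0.5/√3.4 = 0.271 | 0.429 |
| 0.7 | 0.25 | 0.75/√3.4 = 0.407 | 0.804 |
| 0.5 | 0.25 | 0.75/√3 = 0.433 | 0.859 |
| 0 | 0.25 | 0.75/√2 = 0.530 | 0.977 |

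The total can be weaker than its better part, or slightly stronger. The documents give no basis for choosing a row.

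**4. If items were also summed without recoding.** Assumptions: k = 36 equal-variance items, one common factor, inter-item correlation c from 0.2 to 0.5, m items running the opposite way, and a correlation of 0.5 for a correctly keyed total. With s = k − 2m, the correlation of the sum with the factor is s√c / √(k(1 − c) + c s²).

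Example with c = 0.2 and m = 9 (25%): s = 18, giving 8.05/√93.6 = 0.832. Correctly keyed, s = 36, giving 16.10/√288 = 0.949. The ratio is 0.877, so 0.5 becomes 0.439.

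| items reversed | r over c = 0.2 to 0.5 | power at n = 42 |
|---|---|---|
| none, or all recoded | 0.500 | 0.955 |
| 10% | 0.484–0.496 | 0.938–0.950 |
| 25% | 0.439–0.481 | 0.870–0.934 |
| 33% | 0.373–0.453 | 0.719–0.896 |
| 50% | 0 | 0.05 |

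The range runs from no loss to total loss. The documents fix neither the share of reversed items nor whether they are recoded.

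**5. The price of splitting the score.** Section 4.1 states no multiplicity adjustment. Counting one quality-of-life test per hypothesis and assuming independence, six tests at 0.05 give a familywise error of 1 − 0.95⁶ = 26.5%. Two confirmatory scores per hypothesis would give 1 − 0.95¹² = 46.0%.

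**The case against.** The strongest reply is that the documents do not describe SF-36 items at all. Adding up a total does not exclude keying the items first, and the text reads like a translation, so its verb is weak evidence of a raw sum. This stands. A reader might infer that opposite items cancel in the total, or that all six hypotheses lose power. The documents support neither: the recoding loss may be zero (step 4), and the total may even correlate more strongly than one part (step 3).

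A second reply is that the hypotheses concern quality of life as a whole, while physical impairment is already measured by the ODQ and appears in the same six hypotheses. A physical summary would narrow the construct and bring it closer to the ODQ. That is a real cost, and it is why the choice of main score must be stated in advance. It does not rescue a total whose algorithm and direction are undefined.

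A third reply is that the problem is recoverable, because completed questionnaires are kept (section 7.2). That is true, and it makes the change cheap. But section 2.2 states a rule, and following it puts one undifferentiated number per visit into the analysis file.

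**Conclusion.** The point holds as a fault of the analysis variable. Section 2.2 prescribes one examiner-added SF-36 total, and six of the 17 hypotheses in section 4.1 rest on it without naming another score. A correlation with strength, trunk or sensory measures cannot then be assigned to physical or mental health. This rests on one assumption from outside the documents: that the named instrument covers both and has standard scale and summary scores.

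No single figure for lost power is justified. The illustrations run from a small gain to severe loss, depending on inputs the plan does not give. Nor should the point be read as a criticism of n = 42, which reproduces on the plan's own inputs. It should be corrected before analysis; it does not threaten data already collected, provided the questionnaires are kept.

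**What to change.** **Section 2.2.** Replace the added SF-36 total with item-level data entry and the instrument's standard scoring: the scale scores plus the physical and mental summary scores. Name the version and scoring manual, and state the direction of each score and a rule for missing items. Align that rule with section 4.2.

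**Section 4.1.** Add health-related quality of life to the list of subjective parameters. Prespecify one main SF-36 score for each of the six hypotheses, including the pain hypothesis. One workable choice is the physical summary as main score, with the mental summary reported as descriptive or secondary. The number of confirmatory quality-of-life tests then stays at six.

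**Visits already measured.** Rescore them from the questionnaires stored under section 7.2.

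**Cost.** Wording in two sections, extra data entry and a scoring script, with no added burden on patients. The scientific price is a main score narrower than overall quality of life and closer to the ODQ; the plan should say so when it names the score.
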